5.10 Pharmacokinetic variables

██████████ plasma concentrations of ACT-132577 ██████████, measured at steady state at Weeks 2, 4 and 8 in DB treatment period (Period II)

6 DEFINITION OF PROTOCOL DEVIATIONS

PDs include deviations from inclusion and/or exclusion criteria and deviations from the protocol during the conduct of the study, classified as per latest version of PD code list. Each PD is reported in the SDTM DV domain and categorized according to time period:

1. PD at Screening
2. PD during Run-in period
3. PD at Visit 4 / Pre-randomization

4. PD during DB treatment period
5. PD during withdrawal period and follow-up

Each PD is classified as important or not. Only important PDs during time periods 3, 4 and 5 will be summarized by treatment group for the RND set. (All PDs will be listed.)

Note that an important PD does not necessarily lead to exclusion from the PPS [see Section 7.1.6], whereas an unimportant PD may lead to exclusion from the PPS. The subset of PDs *leading to exclusion* from the PPS are:

1. Double-blind treatment duration less than 49 days: PV_PP.535.
2. No or no valid Week 8 SiDBP (hence, no primary endpoint): PV_PP.501 and PV_MM.501.
3. Anti-hypertensive treatment still ongoing at randomization: PV_MM.307.
4. Taking medication during the double-blind treatment interfering with the primary efficacy parameter (SiDBP): PV_MM.503, PV_MM.504, PV_MM.506, PV_MM.507, PV_MM.508, PV_MM.509, PV_MM.534.
5. Compliance with double-blind treatment < 80% or > 120% or treatment not taken as per protocol: PV_PP.502 and PV_MM.515.

Note that exclusion will be done on a subject basis (rather than on subject / visit basis). In this particular study this approach is not unreasonable since PDs 1–5 are related to the 8 week DB treatment period and the primary efficacy endpoint is measured at the end of that period.

The one PD *leading to exclusion* from the Pharmacokinetic (PK) Set [see Section 7.1.6] is that the PK sample for that subject/visit was not taken at trough: PV_MM.512.

7 ANALYSIS SETS

7.1 Definitions of analysis sets

7.1.1 Screened Set

The Screened Set (SCR) includes all subjects who received a subject number.

7.1.2 Run-in Set

The RIS includes all subjects who received at least one dose of SB placebo in Period I.

7.1.3 All Randomized Set

The RND includes all subjects who received a randomization number from the IVRS.

7.1.4 Full Analysis Set

The Full Analysis Set (FAS) includes all subjects in the RND Set who have a baseline mean trough SiDBP. Subjects are evaluated according to the study treatment they have been assigned to (which may be different from the study treatment they have received).

7.1.5 Per-Protocol Set

The PPS includes all subjects from the FAS who have a mean trough SiDBP at Week 8 of Period II and do not have any important PD as defined in Section 6. Subjects are evaluated according to the study treatment they have been assigned to.

7.1.6 Safety Set

The Safety Set (SAF) includes all subjects who received at least one dose of study treatment in Period II. Subjects are evaluated according to the study treatment they have received.

7.1.7 Pharmacokinetic Set

The PK Set includes all subjects from the PPS who had at least one evaluable PK trough sample. Subjects are evaluated according to the study treatment they have received.

8 DEFINITION OF SUBGROUPS

All subgroup analyses will be performed to investigate the consistency of the treatment across subgroups defined by:

Age	< 65 versus \geq 65 years 18–64, 65–84 and \geq 85 years; for European Clinical Trials (EudraCT) Database purposes only
Sex	Female, male
Race	Black or African American; American Indian or Alaska Native; Native Hawaiian or Other Pacific Islander; Asian; White; Other. Categories containing less than 5% of randomized subjects will be considered in the category ‘Other’ for purpose of analysis.
Country	United States (including Puerto Rico, USA); Canada (CAN); Israel (ISR)

9 GENERAL STATISTICAL METHODOLOGY

This section describes the general statistical methodology, independent of which analysis data set is used. These aspects will be addressed in Section 10. SAS and R programming statements are provided to specify the details of the analyses.

9.1 Missing data

All analyses based on the PPS will be based on observed cases (OC). It is acknowledged that the PPS analyses are based on a selected subset of patients who completed the 8 weeks of DB treatment with sufficient compliance and who have no missing data at Week 8. For the assessment of dose-response reliance on this subset was deemed appropriate.

In analyses based on the FAS missing data will be imputed using last observation carried forward (LOCF). This may be justified as a conservative analysis since in this study the majority of patients are expected to improve over time [EMA 2010].

Baseline observation carried forward (BOCF) will be used as a sensitivity analyses for missing data imputation. Another sensitivity analysis is provided by a mixed model which does not impute the missing data and, in that sense, can be seen as a OC analysis. Mixed models are based on the missing at random (MAR) assumption, i.e.: missing data can be fully accounted for by baseline covariates and prior measurements. The MAR assumption is not unreasonable in the hypertension context, although it cannot be proven.

9.2 Dose-response analysis for the primary endpoint

Dose-response data include changes from baseline to Week 8 of DB treatment period in mean trough SiDBP (primary endpoint) and mean trough SiSBP (secondary endpoint). These data will be analyzed using the MCP-Mod approach [Bretz 2005, Pinheiro 2006]. In brief, this methodology consists of two steps:

1. MCPs step to establish a dose-response signal (i.e., the dose-response curve is not flat) using MCPs.
2. Modeling (Mod) step to estimate the dose-response curve and target doses using modeling techniques.

In this study six models have been pre-specified in the protocol for consideration in all MCP-Mod analyses: linear, linear in log (linlog), quadratic, maximum effect (E_{\max}), sigmoidal E_{\max} and logistic. See Table 3 for the parameterization of the dose-response models and Figure 2 as an illustration of their basic shapes. The initial values for the parameters are needed in the MCP step of the procedure. They will be estimated in the Mod step based on the actual data.

[figure not shown]
Table 3 Parameterization of models considered in MCP-Mod analyses

Model	Response*	Initial value(s) for parameters
Linear	$E_0 + \text{delta} \cdot \text{dose}$	NA*
Linear in log	$E_0 + \text{delta} \cdot \log(\text{dose} + 0.5)$	NA*
Quadratic	$E_0 + \text{beta1} \cdot \text{dose} + \text{beta2} \cdot \text{dose}^2$	$\text{beta2}/\text{beta1} = -0.005$
E_{max}	$E_0 + E_{\text{max}} \cdot \text{dose}/(\text{ED50} + \text{dose})$	$\text{ED50} = 50$
Sigmoidal E_{max}	$E_0 + E_{\text{max}} \cdot \text{dose}^h/(\text{ED50}^h + \text{dose}^h)$	$\text{ED50} = 50, h = 0.5$
Logistic	$E_0 + E_{\text{max}}/(1 + \exp\{(\text{ED50} - \text{dose})/\text{delta}\})$	$\text{ED50} = 50,$ $\text{delta} = 50$

Dose = 0, 5, 10, 25 and 50 mg of ACT-132577;

*Not applicable for E_0 , delta (in linear and linlog models), and E_{max}

Figure 2 Dose-response curves considered in MCP-Mod procedure

The Lisinopril group will be excluded from all analyses of the dose-response. Note that the ‘Model means’ on the vertical axis are plotted on a scale from 0 to -1 for illustrative purposes. The actual scale will depend on the endpoint analyzed.

The null hypothesis of ‘no dose-response’ will be rejected if at least one of the six Multiple Contrast Tests (MCTs) has a multiplicity adjusted p-value < 0.05. All statistically significant models (i.e., with an adjusted p-value < 0.05) are fitted in the Mod step and for each model Akaike’s Information Criterion (AIC) is calculated. The smaller the value of AIC (= model deviance + 2 times the number of model parameters), the better the fit. The analysis will be performed using the R-package *DoseFinding* [Bornkamp 2016]. The basic R-code is:

```
library(DoseFinding)
doses <- c(0, 5, 10, 25, 50)
candMod <- Mods(linear = NULL, linlog = NULL, quadratic = -0.005, emax = 50,
               sigEmax = c(50, 0.5), logistic = c(50, 50), doses = doses,
               direction="decreasing")
MMfit <- MCPMod(dose=dose, resp=resp, data=DF, addCovars=~base, models =
candMod, Delta=3)
```

In the Mods function call the candidate models are specified, together with the assumed direction of the effect (decreasing for change from baseline in blood pressure). In the call to the MCPMod function, DF is a data frame with objects dose, resp (for response), and base (for the baseline value) and Delta is a target difference vs placebo (Delta=3 for DBP; Delta=5 for SBP). The object *MMfit* will be summarized to obtain the MCP test, parameter estimates, target dose and AIC. These elements will go in a summary table. The object will be plotted to display the fitted dose-response curves.

Subgroup analyses based on MCP-Mod can be performed by fitting the selected model by subgroup using the *fitMod* function for which the basic R-code is:

```
MMfit1 <- fitMod(dose=dose, resp=resp, data=DF[DF$subg==1,], addCovars=~base,
model=MMfit$selMod)
MMfit2 <- fitMod(dose=dose, resp=resp, data=DF[DF$subg==2,], addCovars=~base,
model=MMfit$selMod)
```

As a supportive analysis to MCP-Mod, change from baseline to Week 8 in DBP and SBP will also be analyzed in an ANCOVA model using the Dunnett test.

```
proc mixed data=dset;
  class treat;
  model outcome=treat base;
  lsmeans treat / adjust=Dunnett diff=control('0') cl;
  where week=8 and treat in (0,1,2,3,4);
run;
```

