- 1. The inclusion criterion 3 has been modified to:
 - Allow selection of subjects based only on DBP (i.e., mean DBP ≥ 90 mmHg) at screening, since 1) the randomization criterion is only based on DBP; and
 2) the primary objective of the study is to explore the dose-response of ACT-132577 on DBP.
 - Align with the Seventh Joint National Committee and European Society of Hypertension Classification [Chobanian 2003, Mancia 2013], which classifies the blood pressure (BP) based on either SBP > 140 and/or DBP > 90 mmHg.
- 2. The randomization eligibility criterion 1 has been modified to:
 - Reduce the lower limit of the DBP in the first part of the criterion to 90 instead of 95 mmHg (i.e., "mean [sitting diastolic blood pressure] SiDBP
 ≥ 90 to < 110 mmHg measured by [office blood pressure measurement] OBPM", and
 - Remove the second part of the criterion: "mean SiDBP values (measured by OBPM) from Visit 3 and Visit 4 must not differ by more than 5 mmHg".

ACT-132577 Essential hypertension Protocol AC-080A201 Version 3 30 May 2016, page 17/112

Confidential

Randomization eligibility criterion 1 (including both parts of the criterion mentioned above) was initially introduced based on experience with classical standard manual OBPM, and landmark studies [e.g., Calhoun 2011].

In this study an automated office BP device (i.e., BpTRU) is used which automatically measures BP 6 times and provides the mean of 5 measurements [see Section 7.2.1.1]. This has several advantages over manual BP measurements by virtually eliminating office-induced increases in BP (white coat effect), improving accuracy, minimizing observer error, and providing a more standardized measurement technique [Myers 2010]. It is also reported that automated OBPM readings are normally 3–4 mmHg lower than manually measured BPs [Edwards 2013].

Therefore, the lower limit of DBP criterion is decreased to 90 instead of 95. This is also more in line with the definition of grade 1 and 2 hypertension (i.e., $SBP \ge 140$ and/or $DBP \ge 90$ mmHg) according to hypertension guidelines.

In addition, due to the above-mentioned advantages (such as improved accuracy) the automated office BP device (i.e., BpTRU) eliminates variability between BP measured at two consecutive visits. Therefore, the second part of the criterion "mean SiDBP values (measured by OBPM) from Visit 3 and Visit 4 must not differ by more than 5 mmHg" has been removed.

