	 Treatment-emergent marked laboratory abnormalities; Changes from baseline to Weeks 2, 4 and 8 of DB treatment period (Period II) in laboratory parameters; Changes from baseline to Weeks 4 and 8 of DB treatment period (Period II) in ECG parameters (PR, QRS, QT, QTcB, QTcF); Changes from baseline to Weeks 2, 4 and 8 of DB treatment period (Period II) in body weight and heart rate. See Section 10.1.1 for definition of 'treatment-emergent'. Pharmacokinetic/pharmacodynamic endpoints Pharmacokinetic / pharmacodynamic endpoints are described in Section 6.2. 					
ASSESSMENTS	in Section 6.3. Refer to the schedule of assessments in Table 1.					
STATISTICAL METHODOLOGY	The Full Analysis Set (FAS) includes all subjects randomized to a study treatment, who have a baseline mean trough SiDBP.					
	The Per-Protocol Set (PPS) includes all subjects from the FAS who have a mean trough SiDBP at Week 8 of DB treatment period (Period II) and do not have any major protocol deviation. Major protocol deviations will be described in the Statistical Analysis Plan.					
	The Safety Set includes all subjects who received at least one dose of study treatment in DB treatment period (Period II).					
	Statistical hypotheses The null hypothesis to be tested is that there is no dose-response for the primary endpoint.					
	H_0 : $\mu_0 = \mu_1 = \mu_2 = \mu_3 = \mu_4$					
	Here, μ_i denotes the mean change from baseline to Week 8 in mean trough SiDBP (μ) for ACT-132577 dose (i) (where $i=0$ corresponds to placebo). A value of $\mu_i < 0$ corresponds to a decrease in SiDBP.					
	The alternative hypothesis is that there is a monotonic dose-response for the primary endpoint.					
	H ₁ : $\mu_0 \ge \mu_1 \ge \mu_2 \ge \mu_3 \ge \mu_4$ and $\mu_i > \mu_j$ for at least one $i > j$ or $\mu_0 \le \mu_1 \le \mu_2 \le \mu_3 \le \mu_4$ and $\mu_i < \mu_j$ for at least one $i > j$					

Note that larger values of μ_i –corresponding to less decrease (or more increase) from baseline to Week 8 in mean trough SiDBP with increasing dose of ACT-132577– are less favorable. The first part of the alternative hypothesis corresponds to ACT-132577 being superior to placebo.

Type I and II errors and power

The type I error (α) is set to 0.05 (two-sided). The type II error is set to 0.10 and therefore the power to 90%.

Primary analysis

The primary analysis will be conducted on the PPS.

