3.2 Study design rationale

This study is designed to select doses to be investigated in the Phase 3 program. The design of this dose-finding study meets the requirements laid out by international guidelines [ICH 2000a, ICH 2000b, EMA 2010] and literature [Rose 1990, Myers 2001].

In accordance with the regulatory guidelines, the study has a placebo run-in period of 4 to 6 weeks. The administration of placebo during this period minimizes bias due to the regression-toward-the-mean phenomenon [EMA 2010]. The placebo run-in period is 4 weeks for anti-hypertensive treatment-naïve subjects at Visit 1. For subjects receiving anti-hypertensive treatment at Visit 1, a 2-week placebo wash-out period is added to the 4-week run-in period. For these subjects the SB placebo run-in period is 6 weeks.

A 2-week SB placebo withdrawal period is introduced at the end of the study to investigate the withdrawal phenomena, i.e., rebound effect on BP.

^{**} Only for women of childbearing potential.

DB = double-blind; EOS = End-of-Study; EOT = End-of-Treatment; FU = follow-up, SB = single-blind, WD = withdrawal.

Essential hypertension Protocol AC-080A201 Version 3 30 May 2016, page 38/112

Confidential

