8.1.3 Visit 3 / Week -1

This visit will be performed at Day -7 ± 4 days.

The subject must not take study treatment at home on the morning of Visit 3.

Visit 3 includes:

- Sitting BP and HR, and standing BP, measured by OBPM device at trough.
- Physical examination and body weight.
- *Laboratory test (i.e., hematology, blood chemistry, and pregnancy test if applicable).
- Reporting of AEs and SAEs.
- Recording of changes in concomitant medications.
- *Assessment of childbearing potential and recording of changes in contraception methods, if applicable.
- *Record the date and time of last study treatment intake before this visit.
- *Check compliance with study treatment.

The investigator checks the exclusion criteria and the following eligibility criterion and decides on the potential eligibility of the subject for the next visit (Visit 4):

- o mean SiDBP measured by OBPM device < 110 mmHg
- 1) If this criterion is not met, the subject must be discontinued from the study. In such case, tests highlighted by * are optional and performed as deemed necessary per medical practice. The investigator has to record the reason of the run-in failure in the eCRF. A follow-up telephone call must be performed in 2 weeks to check any potential AEs/SAEs.
- 2) If the criterion is met, study treatment must be taken at site (i.e., one capsule from each bottle). Record the study treatment intake date and time and instruct subject to continue taking one capsule from each bottle irrespective of food intake every morning between 7:00 and 10.00 a.m. Remind the subject to bring back both bottles to the next visit and not take study treatment on the day of study visit prior to coming to the site.

Essential hypertension Protocol AC-080A201 Version 3 30 May 2016, page 69/112

Confidential

8.1.4 Visit 4 / Day -1 to Day 1

The assessments of this visit will be performed over 2 consecutive days.

Day -1: Visit 4 / Pre-randomization is the end of run-in period. At Day -1, eligibility criteria will be checked. Subjects who are eligible must perform the baseline 24-h ABPM under run-in period study treatment (placebo) before randomization on Day 1.

Day 1: Visit 4 / Randomization is the start of DB treatment period. The DB period consists of Visit 4 / Randomization to 7 / DB-EOT (i.e., Day 1, Week 2, Week 4, and Week 8 visits).

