11.5 Sample size

11.5.1 Sample size justification

In a previous study with macitentan in essential hypertension (AC-055-201) the within-group SD for the change from baseline to Week 8 in SiDBP was 7.4 mmHg (90% CI: 7.0–8.0). In the sample size calculations SDs of 7–9 mmHg are considered.

Essential hypertension Protocol AC-080A201 Version 3 30 May 2016, page 91/112

Confidential

It is assumed that the maximum difference versus placebo is achieved at the highest dose of ACT-132577. For the dose-response curves four scenarios were considered [see Figure 2]. These are, in fact, sigmoidal E_{max} curves.

For the sample size it was required that the power to demonstrate the existence of a dose-response relationship is 90% for each of the four scenarios. A total of 70 subjects per group in the PPS (i.e., 420 subjects in total) satisfied this condition and would also allow for sufficiently precise estimation of the dose-response curve. Assuming a drop-out rate of approximately 20%, a total of 90 patients per group would need to be randomized (i.e., 540 in total).

The power for the MCP-Mod approach to demonstrate the existence of a dose-response relationship with 70 subjects per group (PPS) is given in Table 2 for various combinations of placebo-corrected differences and SDs.

Table 2 Power to demonstrate a dose-response relationship with n = 70 per group (PPS)

	Scenario 1	Scenario 2	Scenario 3	Scenario 4
Delta*	4.9	4.5	4.5	4.0
SD				
7	99%	99%	99%	99%
8	99%	99%	99%	99%
9	98%	96%	98%	97%

^{*}Maximum difference versus placebo (mmHg) PPS = Per-Protocol Set

Conservatively assuming that the difference versus placebo is 4 mmHg and the SD is 9 mmHg, the power for the MCP-Mod approach is > 95% for the four scenarios considered.

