5 DEFINITIONS OF VARIABLES

Baseline assessments refer to the last available measurement before the start of double-blind treatment.

If date and time of the measurement are collected, baseline is the last one up to the start date and time of the double-blind treatment. If only the date is collected, baseline is the last one before the start date of the double-blind treatment. For ABPM baseline is the period from date/time of last run-in placebo intake up to the date/time of the first double-blind treatment intake, i.e., a maximum of 25 hours.

Screening assessments refer to last available measurement before or on run-in start date (Visit 1) before the start of placebo run-in medication.

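### The mandated Visit 3 placebo SiDBP enters no efficacy model; adding it as a second baseline covariate could modestly improve the precision of the primary dose-response

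*SAP*

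**What the plan says.** - **Gate.** Protocol 4.3 and 8.1.4.1 require a Day -1 mean SiDBP of at least 90 and below 110 mmHg for randomization. Under SAP 5.5 each visit value is the mean of five automated readings, the first of six being discarded.
- **Baseline.** SAP 5: "Baseline assessments refer to the last available measurement before the start of double-blind treatment". Protocol 8.2.1 lists no office BP on Day 1, so in practice baseline is the Day -1 value.
- **Visit 3.** Protocol 8.1.3 (Day -7 ± 4) requires: "Sitting BP and HR, and standing BP, measured by OBPM device at trough". Subjects are then on single-blind placebo. The stated use of the SiDBP is a ceiling of 110 mmHg; there is no lower limit.
- **Models.** In SAP 9.2, "DF is a data frame with objects dose, resp (for response), and base (for the baseline value", and the call uses `addCovars=~base`, as do the subgroup fits. The ANCOVA in 9.2 and the models in 9.3 and 10.6.4 likewise have baseline as the only BP covariate (with base by week in 9.3).
- **Rationale.** Protocol 3.2 says of the run-in: "The administration of placebo during this period minimizes bias due to the regression-toward-the-mean phenomenon". The Amendment 2 rationale explains dropping the Visit 3 to Visit 4 agreement rule by saying that the automated device "eliminates variability between BP measured at two consecutive visits".

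**The concern.** A value that both admits a subject and serves as baseline is selected from one side. Some subjects pass because they happened to read high that day, so Day -1 is a noisy measure of usual BP. A second off-drug reading about a week earlier carries further information on that usual level, and the trial already collects it. Visit 3 is the natural choice: Visit 2 takes place only in previously treated subjects, and the Visit 1 reading is taken while those subjects are still on their own medication.

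At stake is the width of the confidence band around the dose-response curve, and so the precision of the minimum effective dose in SAP 10.6.3. Unused baseline information leaves residual variance higher than it need be.

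**Working it through.** **1. Reproduce the plan's own figure.** Inputs: two-sided alpha 0.05 and 90% power (Protocol synopsis); "In the sample size calculations SDs of 7–9 mmHg are considered" (Protocol 11.5.1); doses 0, 5, 10, 25 and 50 mg; the six candidate shapes and four sigmoid Emax truths in the re-estimation SAP code. Simulating the multiple contrast test (400,000 draws, five arms, df = 5n - 5) at SD 9 and averaging over the four truths:

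| n per group | Protocol Table 4 | Simulated |
|---|---|---|
| 47 | 80% | 80.8% |
| 63 | 90% | 90.2% |
| 79 | 95% | 95.2% |

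All 21 cells agree within 1.3 points. At n = 70 and SD 9 the average power is 92.8%.

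**2. Formula for the gain.** Let r be the correlation of each run-in visit with Week 8, and r' that of Visit 3 with Day -1. The ratio of residual variance with both covariates to that with Day -1 alone is

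R = [1 - 2r²/(1 + r')] / (1 - r²).

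The documents give neither r nor r', so all values below are assumptions.

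**3. No shared drift.** Take between-subject SD 6, visit SD 5 and treatment-response SD 4 mmHg.
- Variance of a run-in visit: 36 + 25 = 61. Variance at Week 8: 36 + 25 + 16 = 77. Every covariance: 36.
- Residual on Day -1 alone: 77 - 36²/61 = 55.75.
- Residual on both: 77 - 2 × 36²/(61 + 36) = 50.28.
- R = 50.28/55.75 = 0.90.

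Simulating the Day -1 limits and the Visit 3 ceiling gives 0.91. Across between-subject SD 5-7 and visit SD 5-6, with SD of change 7.7-8.7, R is 0.90-0.94. Adding the Visit 1 criterion of DBP at least 90 (Protocol 4.3), modelled off-drug for simplicity, leaves a cut of about 4-8%. Overall: 4-10%.

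**4. Shared run-in drift.** Take between-subject SD 5, drift SD 4 common to Visit 3 and Day -1, visit SD 3 and response SD 4.
- Run-in variance: 25 + 16 + 9 = 50. Covariance of the two run-in visits: 25 + 16 = 41. Week 8 variance: 25 + 16 + 9 + 16 = 66. Covariance with Week 8: 25.
- R = (66 - 2 × 625/91)/(66 - 625/50) = 52.26/53.50 = 0.98.

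Over drift SD 3-5, with SD of change still 7.7-8.5, the cut is about 1-4%.

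**5. Limits.** As r' approaches 1, R approaches 1. R is also 1 if Visit 3 predicts Week 8 only through Day -1. At the other end, r = r' = 0.7 gives R = 0.83, but with an SD of change of 5.9-6.6, below the planning range.

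**6. Power at n = 70.** Treat SD 9 as the residual SD of the planned model and multiply it by √R:

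| R | Power |
|---|---|
| 1.00 | 92.8% |
| 0.97 | 93.5% |
| 0.95 | 93.9% |
| 0.92 | 94.5% |
| 0.90 | 94.9% |
| 0.83 | 96.2% |

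**7. Subject-equivalent.** Count the five dose-response arms of the PPS: 5 × 70 = 350. Extra subjects = 350 × (1/R - 1): about 4 at R = 0.99, 15 at 0.96 and 39 at 0.90.

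**The case against.** The strongest reply is that nothing is wrong. Baseline-adjusted MCP-Mod and ANCOVA are valid, average power is already 92.8% at n = 70 and SD 9, and the covariates match Protocol 11.3.2.4. SAP 4.2 records a decision taken after database lock, so a new primary covariate would now be a late change. All of this stands. It limits the point to an optional precision gain, worthwhile only if fixed before unblinding.

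Some stronger readings are tempting, and the documents do not support them:

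- *Selection on baseline biases the dose effects.* Regression to the mean acts equally in all randomized arms and cancels in the contrasts. It affects within-arm falls only.
- *The run-in fails in its purpose.* It still removes subjects who were high at Visit 1 and fall below 90 on placebo. Selection does not rest on one reading: Visit 1 also requires at least 90, and each visit value averages five readings.
- *Visit 3 is ignored.* It gates eligibility and has its own window in SAP Table 5. It is absent only from the efficacy models.
- *The gain can be scaled to the 490 randomized.* That number includes lisinopril, which SAP 9.2 excludes from dose-response, and subjects outside the PPS.

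Taken literally, the Amendment 2 remark that the device "eliminates variability between BP measured at two consecutive visits" would mean no gain. The planning SDs of 7-9 mmHg show substantial variation over eight weeks but do not settle how closely two adjacent visits agree.

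**Conclusion.** The point holds as a modest efficiency suggestion. The Day -1 value is both gate and baseline, and a comparable placebo reading from about a week earlier is left out of every efficacy model. The planned test is valid.

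The expected reduction in residual variance is about 4-10% without shared run-in drift (towards the lower end once the Visit 1 criterion is counted), about 1-4% with it, and possibly nil. That is roughly 0 to 3 power points at n = 70 and SD 9. These figures rest on assumed variance components. A reader might infer that precision is bound to improve; the documents cannot show that, because they report no between-visit correlation.

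**What to change.** Before unblinding:

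- Use `addCovars=~base+v3` in SAP 9.2, including the subgroup fits.
- Add v3 to the ANCOVA and mixed models of SAP 9.2, 9.3 and 10.6.4, with v3 by week wherever base by week appears. Use Visit 3 SiSBP for the SiSBP models.
- Take Visit 3 from the SAP Table 5 window (Day -17 to -4). Protocol 8.1.4.1 puts Day -1 at 7 ± 2 days after Visit 3, that is Visit 3 on Day -10 to -6, so compliant visits fall inside it.
- Set a missing Visit 3 value to the Day -1 value, so that no subject drops out of the primary model.
- Record the change in SAP 4.1 and keep the protocol's single-covariate model as a sensitivity analysis.

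The cost is one degree of freedom in the primary model (about 350 subjects at the planned size), one simple imputation rule, one added sensitivity run and a documented departure from the protocol's covariate list. No new data are needed. If the treatment codes are already open, the two-covariate model should be shown only as a supplementary analysis and labelled post hoc.
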